1.4.7 Preliminary Data

1.4.7.1 Prostate Imaging for Radiation Treatment Planning at the University of Miami

MRI simulation of the prostate is routinely performed. T2, T1 non-contrast, T1 DCE and DWI MRI sequences are obtained with size and spacing suitable for fusion with the CT for treatment planning. The MRI exam of the prostate is performed at the University of Miami on a 1.5T or 3.0T MR scanner with a body coil. In **Figure 3** an axial T2w MRI of a male pelvis is shown: resolution $0.7 \times 0.7 \times 2.5$ mm; Rectangular Field of View: 360×264 mm; slice thickness - 2.5 mm (no gap); 72 slices; repetition time (TR) 6300 ms/echo time (TE) 112 ms; flip angle 120° . The arrows point to a hypointense area in the right peripheral zone suspicious for tumor (**Figure 3A**). The prostate, centered in the red box, is presented in the series of T1-weighted gradient echo sequence MR images (**Fig 3B**), acquired with identical spatial resolution, spacing and image size as the T2w MRI. Prior to contrast material injection, one set of MR images were acquired as a pre-contrast image T1 data set. The rest of the data were acquired following intravenous bolus injection of a paramagnetic gadolinium chelate - 0.1 mmol of gadopentetate dimeglumine per kilogram of body weight. The contrast is administered with a power injector at 2.5 mL/s and followed by a 15-mL saline flush. The image sequence parameters were: TR/TE 5.1/2.3 ms; flip angle 10° . Eleven post-contrast imaging datasets (37 sec each) were collected.

1.4.7.2 Delineation and Visualization of Prostate Cancer in DCE-MRI

Our software co-registers the DCE data with the T2-weighted MRI. The Region of Interest (ROI) is manually outlined on each axial slice. Let I_{ij} denote the ROI on the i^{th} axial slice at j^{th} time point and let \mathbf{D} be the

matrix of the DCE-MRI data: $\mathbf{D} = \begin{pmatrix} I_{1,1} & \dots & I_{1,m} \\ \vdots & \ddots & \vdots \\ I_{n,1} & \dots & I_{n,m} \end{pmatrix}$ where

n is the number of slices within the ROI and m is the number of acquired time series. Principal Component Analysis (PCA) is applied to \mathbf{D} to determine k – the number of significant Principal Components (PCs). The data is further analyzed with the constrained non-negative matrix factorization (cNMF)⁴ method, which assumes each image to be a mixture of k tissue

[figure not shown]
[figure not shown]

Figure 4. (A) Basic signal-to-time patterns determined within the prostate in DCE-MRI studies of a patient with prostate cancer; (B) Their corresponding weights displayed as heat maps in one slice of the prostate.

components with individually associated basic contrast-to-time curves. cNMF determines representation of D as a product of k basic contrast signatures (S) and their weights (W), i.e.

$$D \approx W \times S, \text{ where } W = \begin{pmatrix} W_{1,1} & \dots & W_{1,k} \\ \vdots & \ddots & \vdots \\ W_{n,1} & \dots & W_{n,k} \end{pmatrix} \text{ and } S = \begin{bmatrix} S_1 \\ \vdots \\ S_k \end{bmatrix}$$

under the constraint that all elements of W

and S are non-negative. When PCA is applied to D , four of the higher order PCs contained structural information (data not shown). Further, cNMF was applied to D seeking 4 solutions ($k=4$). The identified four temporal curves (S) and their corresponding weights are shown in **Figure 4**. The first curve in **Figure 4** shows the characteristic tumor tissue's temporal signature: relatively fast contrast uptake and wash-out (S_T). The highest intensities of its corresponding weight W_T (**Figure 4B**, top image) indicate that the location of this pattern coincides with the hypointensity on the T2w (**Figure 5**). The second curve is almost constant throughout the experiment and its spatial location indicates that it is associated with a nodule, possibly a cyst. The last two patterns are related to tissues with a relatively slow contrast uptake.

We investigated several schemes for thresholding the tumor pattern map (W_T) so that the target for radiation is clearly depicted on the anatomical image. In **Figure 5** three thresholded maps are presented: (1) All values in W_T larger than the lower limit of the fourth quartile; (2) $W_T > \text{mean}(W_T) + 1.64\text{stdev}(W_T)$; and (3) $W_T > \text{mean}(W_T) + 2\text{stdev}(W_T)$. The thresholded maps are overlaid with the corresponding T2w image and the green contour depicts the area of hypointensity suspicious for tumor. All methods for thresholding performed quite well with the last being the most conservative. For this project we will use the second method resulting in a display of values from the 95th percentile and higher, assuming that W_T is normally distributed. The last image in **Figure 5** depicts the area of the tumor with a rhomboid-like structure (3-5 mm sides) formed by the highest intensities in W_T . This area potentially could guide the placement of one high-dose cylindrical LEAD region of and it is clearly depicted in all displays of the thresholded W_T .

1.4.7.3. LEAD Dose Delivery

To affirm deliverability and accuracy of the desired radiation dose we carried out the following experiment: a Cyberknife-based LEAD RT dose plan was delivered to a 3D phantom with five small dose cylinders, and a maximum dose of 15 Gy at the center of each dose cylinder (**Figure 6A, B**). The plan was

[figure not shown]

Figure 6.(A-B) Cyberknife-based LEAD dose plan, delivered to a 3D phantom. (C) Dosimetric verification, using Gafchromic films. (D) Computational (dash) and measured (color bands) dose.

developed on a clinically commissioned commercial planning system without any software or hardware modification. Wide-range Gafchromic films were employed for dosimetric verification (**Figure 6C**). Good agreement (3% and <1 mm) between the measurements and the plans was obtained, as shown in **Figure 6D** (computation in dash vs. measurement in color bands). Only a small amount of the “surrounding normal tissue/critical structures” received 2-3 Gy or less.

The results show that it is feasible to deliver the desired cylindrical high dose LEAD RT dose distributions with “peak-to-valley” characteristics, the key to triggering the expected bystander effects.

1.5 Quality of Life

IMRT is an advanced technology that delivers the total radiation dose in a pattern that closely matches the shape of the target volume in three dimensions and avoids normal tissues. This sparing of normal tissue, which is best accomplished using IMRT, decreases bladder and rectal toxicities and improves quality of life after prostate cancer therapy.⁷¹⁻⁷⁶ Reports by Zelefsky et al^{77,78} indicate that treatment with IMRT reduces the incidence of late grade 2 rectal toxicity compared to 3DCRT. The 8 year risk of \geq grade 2 rectal bleeding was 1.6%. The 8-year rate of \geq grade 2 urinary toxicity was 12%. The impact of IMRT has been greatest on the reduction in rectal toxicity, as compared to 3DCRT.

In the study proposed here all patients will receive IMRT. The Quality of Life (QOL) assessments will provide unique data on the effects of LEAD RT on QOL. We have selected a group of measures that have been used extensively in prostate cancer populations.

As an index of Prostate Cancer-Specific Anxiety we will administer the Memorial Anxiety Scale for Prostate Cancer patients (MAX-PC). The MAX-PC is an 18-item instrument designed to detect symptoms of anxiety in prostate cancer patients. It is designed to evaluate three separate aspects of prostate cancer specific anxiety on 3 subscales: anxiety related to prostate cancer in general (prostate cancer anxiety subscale), anxiety specifically centered around PSA testing (PSA anxiety subscale) and fears of cancer recurrence (fear of recurrence subscale). The MAX-PC demonstrated high internal reliability with a Cronbach's alpha of 0.89, with subscale reliabilities between 0.59-0.90 and has been validated in prostate cancer patient samples.⁸⁰

Prostate Cancer-specific Quality of Life and Health-Related Quality of Life will be measured with the Expanded PCa Index Composite-SF-12 (EPIC-SF12)⁸¹ Development of the EPIC-SF12 was based on the widely used University of California Los Angeles Prostate Cancer Index and has been used extensively to assess post-treatment related dysfunction among PCa patients. A sub-section of this survey yields a score for the following Health Related Quality of Life subscales: physical functioning, role limitations due to physical functioning, body pain and general health. The mental summary score is comprised of vitality, social functioning, role limitations due to emotional functioning and mental health subscales. The EPIC-SF12 has demonstrated excellent reliability (i.e., Cronbach's $\alpha > .91$) across sexual function and sexual bother composites. The EPIC-SF12 questionnaire will be used to measure changes in QOL over time.^{82,83}

All participants will be assessed at baseline (prior to initial biopsy), during the last week of RT, at 6 weeks, 3 months, 9 months, 15 months and then yearly to 5.25 years. Psychosocial assessments will be conducted by a trained and fully-bilingual clinical coordinator/research nurse with experience in conducting psychosocial assessments in prostate cancer populations. We will make every effort to pair our psychosocial assessment visits with scheduled clinic appointments to reduce participant burden. The psychosocial battery will last between 30-40 minutes. All assessments will be conducted in private rooms in our clinics. All psychosocial data will be deidentified and only coded by participant number. Should a participant display any

significant signs of distress (e.g. high levels of anxiety, depressed mood or spontaneous comments suggesting a need for psychosocial care), we will refer participants to appropriate psychosocial resources within our medical center.

Another measure of urinary function is the International Prostate Symptom Score (IPSS).⁸⁴ This scoring system has been established as a measure of radiation morbidity in patients treated for prostate cancer⁸⁵⁻⁸⁸ and will be administered prior to treatment, at the end of radiotherapy and at each follow-up visit. Questionnaires are available in English and Spanish.

1.6 Age, Gender and Ethnicity

Prostate cancer is a disease of adult men with exceptionally few diagnosed at <35 years of age. We have chosen an age range of ≥ 35 to ≤ 85 years, which represents nearly all patients treated locally with radiotherapy for adenocarcinoma of the prostate. Therefore, women and children are not candidates for this protocol. It is estimated that approximately 40% of patients are White, 24% are African American, 35% are Hispanic and 1% are other based upon standard NIH definitions.

2.0 OBJECTIVES

2.1 Primary Objective

- To determine the feasibility and toxicity of LEAD RT in a Phase I clinical trial.

2.2 Secondary Objectives

- To measure the risk of leaving tumor cells in the prostate after LEAD RT by obtaining serial post-RT MRI's (3 months and 9 months, and within 2 months of the post-treatment prostate biopsy).
- To quantify biomarker expression in different prostate tumor regions, comparing specifically the multiparametric suspicious and unsuspecting regions.
- To determine the proportion of study patients with positive prostate biopsies at 2-2.5 years after completion of therapy as a preliminary indication of the efficacy.
- To report failure-free (biochemical and clinical progression) and overall survival.
- To assess Health-Related Quality of Life (HRQOL) in the study patients.

3.0 PATIENT SELECTION

3.1 Inclusion Criteria

- A. Biopsy confirmed adenocarcinoma of the prostate.
- B. T1-T3a disease based on digital rectal exam (DRE).
 - a. T3a disease based on MRI is acceptable (no evidence of frank (clear-cut) SV involvement or invasion of bladder or rectum).
- C. Gleason score 6-10.
- D. Patients with Gleason score ≥ 8 must be offered long term androgen deprivation therapy (ADT) and refuse such treatment because only 4-6 months (+/- 2 months) (short term ADT) is permitted (not required) on this protocol. The ADT is recommended to begin after fiducial marker placement; however, ADT is permitted to have been started up to two months prior to the signing of consent. All patients in this protocol may (not required) be treated with 4-6 months (+/- 2 months) of ADT, at the discretion of the treating physician.
 - a. Gleason ≥ 8 must have <40% of the tissue involved with Gleason 8 in the biopsy specimen.

- E. PSA \leq 30 ng/mL within 3 months of enrollment. If PSA was above 30 and dropped to \leq 30 with antibiotics, this is acceptable for enrollment.
- F. No previous pelvic radiotherapy.
- G. No previous history of radical/total prostatectomy (suprapubic prostatectomy is acceptable).
- H. No concurrent, active malignancy, other than non-metastatic skin cancer or early stage chronic lymphocytic leukemia (well-differentiated small cell lymphocytic lymphoma). If a prior malignancy is in remission for \geq 5 years then the patient is eligible.
- I. Identifiable multiparametric-MRI tumor lesion or lesions, that total in volume $<$ 33% of the prostate
 - a. Multiparametric MRI of prostate and pelvis is required prior to protocol consideration.
 - b. If contrast not given, the point dose on the ADC map should be $<$ 1000.
- J. Ability to understand and the willingness to sign a written informed consent document.
- K. Zubrod performance status $<$ 2.
- L. Willingness to fill out quality of life forms.
- M. Bone scan negative if PSA $>$ 15 ng/mL or Gleason \geq 8 disease. A questionable bone scan is acceptable if other imaging tests are negative for metastasis.
- N. Serum testosterone is within 40% of normal assay limits (e.g., $x=0.4$ *lower assay limit and $x=0.4$ *upper assay limit + upper assay limit), and taken within 4 months of enrollment. Patients who have been started on ADT prior to signing consent are not required to have a serum testosterone at this level prior to signing consent; but, a serum testosterone prior to fiducial marker placement is recommended.
- O. Serum liver function tests (LFT) are taken within 3 months of enrollment.
- P. Complete blood counts are within taken within 3 months of enrollment.
- Q. Age \geq 35 and \leq 85 years.

3.2 Exclusion Criteria

- A. $>$ T3a disease on digital rectal exam or $>$ T3a disease clearly identified by MRI.
- B. Gleason score $<$ 6.
- C. \geq 40% Gleason 8-10 tumor, over the total tissue including other tumor and normal tissue. For example: (Gleason 8-10 tumor length/other biopsy tissue length)*100 = \geq 40%.
- D. Androgen deprivation therapy longer than 8 months. Androgen deprivation timing is for the Luteinizing hormone-releasing hormone (LHRH) agonist portion only and not when anti-androgen is started beforehand with the purpose of counteracting the surge in testosterone from the LHRH agonist
- E. PSA $>$ 30 ng/mL within 3 months of enrollment.
- F. Unable to obtain a 1.5T or 3.0T multiparametric MRI of the pelvis and prostate with or without contrast.
- G. Unidentifiable multiparametric MRI tumor lesion.
- H. Identifiable multiparametric-MRI tumor lesions, that total in volume \geq 33% of the prostate.
- I. Previous pelvic radiotherapy.
- J. Previous history of radical prostatectomy.

- K. Concurrent, active malignancy, which is not non-metastatic skin cancer or early stage chronic lymphocytic leukemia (well-differentiated small cell lymphocytic lymphoma). If a prior malignancy is in remission for < 5 years then the patient is not eligible.
- L. Zubrod performance status ≥ 2 .
- M. Inability to understand or unwilling to sign a written informed consent document
- N. Unwilling to fill out quality of life/psychosocial forms.
- O. Bone scan is positive and other imaging tests confirm a suspicion of metastasis from prostate cancer.
- P. Serum testosterone is not within 40% of normal assay limits taken within 4 months of enrollment (only applicable to patients not started on ADT prior to signing consent).
- Q. Serum liver function tests (LFTs) are not taken within 3 months of enrollment.
- R. Complete blood counts are not taken within 3 months of enrollment.
- S. Age <35 and >85 years.

3.3 Enrollment Procedures

To enter a patient, the investigator or study team will contact the CRS representative. All eligibility requirements must be reviewed prior to the patient entering the study. The following information must be provided to the CRS representative:

- 1) Completed and signed eligibility checklist.
- 2) All pages of the original signed informed consent forms (ICFs), including HIPAA form B.
- 3) Relevant source documents such as: subject medical history and physical exam; admission or discharge notes; diagnostic reports; pathologic confirmation of diagnosis by University of Miami pathologists (UM review) and relevant subject-specific communication.
- 4) To assure compliance with early stopping for toxicity, the monitor will inform the study team when the forth patient may be enrolled.

3.3.1 Cancellation Guidelines

If a patient does not receive protocol therapy, the patient may withdraw. Patients who are enrolled on study but not treated with the LEAD component of the protocol will be excluded from all analyses.

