9.1 Definitions

- *Feasibility*: The proportion of enrolled patients for whom LEAD RT dose can be successfully administered following MRI-guided planning.
- *Acute toxicity*: Grade 2 or higher treatment-related acute GU/GI toxicity occurring during treatment and within 30 days of completing treatment. The severity of the reactions to the treatment is scored according to the criteria outlined in Appendix II.
- *Late toxicity*: Delayed toxicities are usually related to urinary, rectal, and sexual function. The anticipated urinary and rectal toxicities and severity criteria are shown in Appendix II.
- *Biopsy failure rate*: The proportion of positive biopsy findings among patients without clinical or biochemical failure 2-2.5 years after completing study treatment.
- *Biochemical failure-free interval (BFFI)*: The elapsed time from study enrollment to first documented evidence of biochemical failure ($PSA \geq \text{nadir}+2$). In the absence of biochemical failure, follow-up time will be censored at the date of last documented biochemical failure-free status.
- *Biochemical failure (BF) rate*: The cumulative incidence of BF allowing for competing risk as needed.
- *Biochemical failure-free survival (BFFS)*: The elapsed time from study enrollment to first documented evidence of biochemical failure or death from any cause, whichever occurs first. In the absence of any event defining biochemical failure, follow-up time will be censored at the date of last documented biochemical failure-free status.
- *Failure-free interval (FFI)*: The elapsed time from study enrollment to first documented evidence of biochemical or clinical failure. Clinical failure is defined as local failure due to newly identified extension outside of the prostate after initial regression, or urinary obstructive symptoms with carcinoma found at TURP or regional/distant failure due to radiographic evidence metastasis (nodal or hematogenous spread). In the absence of any event defining failure, follow-up time will be censored at the date of last documented failure-free status.
- *Failure rate*: The cumulative incidence of biochemical or clinical failure allowing for competing risk as needed.

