13.0 DATA REPORTING

Data will be submitted according to the protocol requirements for ALL patients registered. Patients for whom documentation is inadequate to determine eligibility will generally be deemed ineligible.

A list of forms to be submitted, as well as submission schedule, may be found in Appendix IV.

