14.0 STATISTICAL CONSIDERATIONS

14.1 Sample Size/Accrual Rate

Twenty five (25) patients will be enrolled over a two-year period, subject to early stopping rules for safety (grade 3 or higher treatment-related acute GU/GI toxicity) and feasibility (LEAD eligibility). Study size is intended to provide initial evidence of safety and feasibility of the proposed treatment as a basis for planning Phase II efficacy trial.

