14.2 Analysis Plan

Study findings will include descriptive statistics summarizing patient baseline characteristics, RT planning parameters and treatment received⁹⁴. A detailed safety profile will be provided consisting of lists and tabulations of all adverse events indicating type, grade, attribution to treatment and time of onset relative to treatment according to CTCAE standards. This will be done separately for acute and late toxicity (see Section 9.1). Patient level summaries will include worst grade toxicity and the number and duration of treatment delays attributable to toxicity.

Feasibility will be assessed by reporting the proportion of enrolled patients who are administered LEAD dose following successful MRI-guided planning and corresponding 95% confidence interval (CI) using the exact binomial method. The same method will be used to estimate the two-year positive biopsy rate defined as the proportion of positive biopsy findings among patients without clinical or biochemical failure two years after completing study treatment.

Clinical outcome will be further assessed by estimating the rate of biochemical failure, as defined in Section 9.1, using the method of cumulative incidence allowing for competing risk of death without biochemical failure. Biochemical failure free survival will be estimated by the Kaplan Meier method. Similar analysis will be provided for the combined rate of biochemical and clinical failure (cumulative incidence) and failure free survival (Kaplan Meier). Although death of study patients during the planned follow up period is expected to be rare and not attributable to prostate cancer, we include these survival endpoints (biochemical failure-free, failure-free, and overall survival) for completeness.

We will summarize the scores of QOL assessments with descriptive statistics and apply mixed effects modeling to evaluate changes over time.

Finally, to the extent permitted by available data from baseline biopsies, exploratory analysis will be performed to investigate the relationship between the level of biomarker expression in tumor tissue within vs. outside the DCE-MRI determined region and the correlation between these measures and Gleason score. Analysis of the sequential imaging studies will correlate the presence/absence of DCE enhancing area and its volume with biopsy positivity at 2 – 2.5 years. We will attempt to establish the ability of MRI for early assessment of RT outcome.

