As an additional safeguard, the first three patients enrolled on study will be observed for 30 days following treatment completion of the third patient before enrollment is continued (fourth patient). If two or three of the first three study patients have grade 3 or higher GI/GU toxicity within 30 days of treatment completion, enrollment will be suspended pending DSMC review. If none or one of the first three patients enrolled on study have grade 3 or higher GI/GU toxicity

within 30 days of treatment completion, enrollment will continue without restriction on the interval between successive enrollments.

Posterior probabilities used to derive the preceding table are calculated under a prior beta distribution with parameters $\beta_1 = 0.2$ and $\beta_2 = 1.8$, which corresponds to an expected rate of 15% based on prior information roughly equivalent to having studied 2 patients^{96,97}. Furthermore, this prior distribution assigns a small a priori chance (32%) to the possibility that the true rate of unacceptable toxicity is 15% or greater.

Table 3. Stopping Rules For Lack of Feasibility

Number of Patients ineligible For LEAD	Total Patients enrolled and completed CT simulation	Observed LEAD ineligibility rate
2	3	67%
3	4 to 6	≥50% (3 of 6)
4	7 to 10	≥40% (4 of 10)
5	11 to 13	≥38% (5 of 13)
6	14 to 17	≥35% (6 of 17)
9	18 to 25	≥35% (9 of 25)

Stopping rules for lack of feasibility

Similarly, for purposes of monitoring the feasibility of delivering LEAD RT, we consider the proportion of patients enrolled on study for whom it is not possible to deliver LEAD RT as determined from CT/MRI simulation and planning, referred to as the *LEAD ineligibility rate*. The LEAD treatment will not be delivered if the summed dose of LEAD and conventional treatment to critical structures exceeds tolerance. Early stopping due to infeasibility of the proposed study treatment will be considered if there is evidence that the rate of LEAD ineligibility exceeds

20%. Specifically, we suggest as a guideline for early termination a posterior probability of 90% or higher that the rate of unacceptable toxicity exceeds 20%. **Table 3** shows specific instances where this guideline is met, thus suggesting early termination due to early evidence of LEAD infeasibility.

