14.5 Reporting and Exclusions
N/A

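### Section 3.3.1 excludes enrolled patients not given LEAD from every analysis, yet these patients are the failures in the primary feasibility endpoint

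*Combined protocol and SAP*

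**What the plan says.** Four parts of the protocol bear on who is counted.

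- **Exclusion rule, section 3.3.1 (Cancellation Guidelines):** "Patients who are enrolled on study but not treated with the LEAD component of the protocol will be excluded from all analyses". No analysis is exempted.
- **Endpoint definition, section 9.1:** feasibility is "The proportion of enrolled patients for whom LEAD RT dose can be successfully administered following MRI-guided planning".
- **Analysis, section 14.2:** "Feasibility will be assessed by reporting the proportion of enrolled patients who are administered LEAD dose following successful MRI-guided planning", with an exact binomial 95% confidence interval.
- **Monitoring, section 14.4:** the LEAD ineligibility rate is "the proportion of patients enrolled on study for whom it is not possible to deliver LEAD RT", judged from simulation and planning. The same section gives the mechanism: "The LEAD treatment will not be delivered if the summed dose of LEAD and conventional treatment to critical structures exceeds tolerance".

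Section 2.1 names feasibility and toxicity together as the primary objective. Section 14.1 adds: "Study size is intended to provide initial evidence of safety and feasibility of the proposed treatment", as a basis for planning a Phase II trial. The place where a reader would look for analysis exclusions, "14.5 Reporting and Exclusions", contains only N/A.

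**The concern.** Fiducial placement, simulation and planning all come after enrollment. A patient whose plan fails the summed-dose check is therefore, by design, enrolled and not treated with LEAD. Section 14.2 counts that patient in the denominator and not in the numerator. Section 3.3.1 takes the same patient out altogether. The two rules cannot both be followed for the feasibility analysis.

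An analyst who follows 3.3.1 would report 100% feasibility with a narrow interval, and the figure would carry no information about whether LEAD can be delivered. That figure is meant to inform the decision on a Phase II trial.

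A smaller wording difference affects the same count. Section 9.1 speaks of patients to whom LEAD *can* be given, section 14.2 of patients to whom it *is* given. A patient who withdraws before planning is plainly not a success under 14.2, but is not clearly a failure under 9.1.

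**Working it through.** **Inputs.** Planned enrollment is 25 (14.1). The interval is exact binomial, 95% (14.2). The monitoring limit for LEAD ineligibility is 20% (14.4), and its complement is 80% delivery. The prior for ineligibility is Beta(0.4, 1.6) (14.4). The documents give no expected number of patients not given LEAD, so the counts below are assumed.

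**The plan's own figure.** Under Beta(0.4, 1.6) the mean is 0.4/(0.4 + 1.6) = 0.20 and P(rate > 0.20) = 0.361. These match the stated 20% and 36%. The plan therefore expects that some enrolled patients may not be able to receive LEAD.

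**Formula.** For x treated out of n, the exact 95% limits are:

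- lower = the 0.025 quantile of Beta(x, n − x + 1)
- upper = the 0.975 quantile of Beta(x + 1, n − x)

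When x = n = m, the upper limit is 1 and the lower limit reduces to 0.025^(1/m).

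**Results with 25 enrolled.**

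| Not given LEAD | Enrolled denominator (9.1, 14.2) | Section 3.3.1 as written |
|---|---|---|
| 0 | 25/25 = 100% (86.3-100%) | 25/25 = 100% (86.3-100%) |
| 1 | 24/25 = 96% (79.6-99.9%) | 24/24 = 100% (85.8-100%) |
| 3 | 22/25 = 88% (68.8-97.5%) | 22/22 = 100% (84.6-100%) |
| 5 | 20/25 = 80% (59.3-93.2%) | 20/20 = 100% (83.2-100%) |
| 8 | 17/25 = 68% (46.5-85.1%) | 17/17 = 100% (80.5-100%) |

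In each row with at least one untreated patient, the interval under 3.3.1 lies wholly above 80%, while the enrolled-patient interval contains 80%.

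**Coverage if true delivery were 80%** (assumed, with 25 enrolled and no early stopping). The lower limit 0.025^(1/m) is 0.7941 at m = 16 and 0.8049 at m = 17, so the interval under 3.3.1 contains 0.80 only if m ≤ 16. With m ~ Binomial(25, 0.8), P(m ≤ 16) = 0.0468. The nominal 95% interval would thus cover the true value 4.7% of the time. The exact interval on x/25 covers it 97.9% of the time.

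**Monitoring.** If 3.3.1 were also applied to Table 3, the number of ineligible patients would always be zero and the feasibility rule could never trigger.

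**The case against.** The best defence is that the specific text governs the general. Section 3.3.1 is an enrollment-procedure clause under a cancellation heading, and the sentence before it is about withdrawal. The statistical sections state the enrolled denominator twice, and 14.4 counts the ineligible patients during accrual. The literal reading would empty all three provisions, so a careful analyst would use x/enrolled. This is very likely what was intended, and it limits the practical risk. It does not remove the conflict: the exclusion covers all analyses without qualification, and no section ranks the two rules.

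Table 3 protects the trial only in part. If true ineligibility were 20%, all 25 completed simulation and Table 3 were applied after each patient, the trial would stop early about 24% of the time. The coverage figures leave that out, so they show what the wrong denominator does and are not operating characteristics of this trial. Table 3 also does not govern the final estimate in 14.2.

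The 80% mark is a monitoring limit, applied through a 90% posterior probability to patients who completed CT simulation. The plan sets no success threshold for the final estimate, so 80% serves here only as a reference. With one untreated patient, the enrolled interval reaches below it only just (79.6%).

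Finally, the wording in 9.1 could be read as technical deliverability, in which case a personal withdrawal would not be a failure. That reading is possible, but 14.2, which specifies the analysis, already counts patients actually given LEAD. Matching 9.1 to it adds no new endpoint.

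**Conclusion.** The concern holds. As written, 3.3.1 makes the feasibility estimate 100% by construction and contradicts the endpoint definition and the analysis plan. The bias equals the proportion of enrolled patients not given LEAD: nothing if all are treated, and 4, 12 or 20 percentage points with 1, 3 or 5 untreated out of 25. These counts are illustrative. The coverage comparison also assumes 80% true delivery and no early stopping.

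This should be fixed, because one untreated patient is enough to change half of the primary result. It is not graver than that, because the intended denominator can be recovered from 9.1 and 14.2 and the whole defect is a missing exception.

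**What to change.** 1. **Section 3.3.1:** replace the exclusion sentence with: *Enrolled patients who do not receive LEAD are left out of the toxicity, biopsy, biomarker, clinical outcome and QOL analyses. They stay in the denominator of the feasibility analysis (9.1, 14.2) and in feasibility monitoring (14.4). The reasons LEAD was not given are tabulated with these patients' baseline characteristics.*
2. **Section 9.1:** define the feasibility numerator as enrolled patients who are actually given LEAD, to match 14.2.
3. **Section 14.5:** replace N/A with a reference to 3.3.1.

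Table 3 can keep its own denominator (enrolled with CT simulation completed), because it monitors technical ineligibility and not final delivery.

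**Cost.** Three short text edits and no extra patients. Section 13.0 already provides: "Data will be submitted according to the protocol requirements for ALL patients registered". Section 15.5, however, requires a CRF only for patients who received some study treatment, so the team should confirm that an existing form records why LEAD was not given. The one real downside is that the feasibility figure may look less favourable, since a withdrawal before LEAD counts as not administered. The table of reasons will show how much of the shortfall is due to that.
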